This is a non-interventional prospective, single center, bilateral, non-randomized, open-label, observational clinical study. All patients will have had bilateral implantation of an Eyhance IOL at the time of cataract surgery. These patients will then be assessed in the 1–6-month post-operative period. Patients will be grouped into two arms: “distance with minimal intermediate” and “distance with enhanced intermediate/near” based on mean photopic binocular BCDVA and DCIVA (at 66 cm) of patients with bilateral Eyhance IOLs corrected to plano sphere. The “distance with minimal intermediate” group is defined by BCDVA of 0.1 logMAR or better but a DCIVA of 0.4 logMAR or worse. The “distance with enhanced intermediate/near” is defined by BCDVA of 0.1 logMAR or better and a DCIVA of 0.3 logMAR or better. In addition to binocular BCDVA and DCIVA, monocular measurements will be obtained as well. The two groups will be compared to assess which patient biometric properties (such as spherical aberration, q value, pupil size, etc) lead to an overall increase in near or intermediate vision as well as overall patient satisfaction. Biometric data will be obtained from the Zeiss IOL Master 700, Atlas 9000, and the iDesign.

Duration:

3 months or longer to meet required enrollment.

Administration:

Patients with previously implanted bilateral Eyhance IOLs will be offered the opportunity to participate in the study.

Visit Schedule:

All subjects will undergo 1 visit. At the study visit and after informed consent, the subjects' demographic information will be collected, and the subject will have the following testing:

- 1) Manifest refraction
- 2) Best corrected distance visual acuity
- 3) Distance corrected intermediate visual acuity
- 4) Distance corrected near visually acuity
- 5) Binocular best corrected distance visual acuity
- 6) Binocular distance corrected intermediate visual acuity
- 7) Binocular distance corrected near visually acuity
- 8) Pupil measurements (photopic and/or mesopic – automated and manual)
- 9) Review or remeasurement of biometry (IOL Master 700 or Atlas 9000 topography)
- 10) iDesign measurement

STUDY POPULATION CHARACTERISTICS:

Condition

Patients with healthy eyes and bilateral implantation of Eyhance IOLs.

Number of Subjects:

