Per Green, for multiple variables in a regression analysis, $N = 50 + 8(m)$ per arm should be sufficient for appropriate power, assuming a beta of 0.2 and an alpha of 0.05 for a power of 80%. Assuming 6 variables (pupil size, q value, spherical aberration, AC depth, axial length, average K power), approximately 110 patients (220 eyes) will be required.

Source: Green, Samuel B. "How Many Subjects Does It Take To Do A Regression Analysis." *Multivariate behavioral research* 26 3 (1991): 499-510 .

Inclusion/Exclusion Criteria (all study criteria apply to each study eye unless otherwise indicated):

Inclusions

- 1) Adults, 40 years of age having already undergone uncomplicated cataract removal by phacoemulsification with a clear corneal incision in both eyes.
- 2) Implantation of bilateral Eyhance IOLs (DIB00/DIU***).

- 3) Able to comprehend and willing to sign informed consent and complete all required testing procedures
- 4) Best Corrected Distance Visual Acuity (BCDVA) projected to be 0.10 logMAR (Minimum Angle of Resolution) or better
- 5) Clear intraocular media
- 6) Minimum of two weeks post YAG capsulotomy to treat PCO

Exclusions

Subjects will not be permitted to enroll in this study if they meet any of the following exclusion criteria:

- 1) Any corneal abnormality, other than regular corneal astigmatism (as determined by pre-operative testing) that in the opinion of the investigator would confound the outcome(s) of the study
- 2) Any complication during cataract surgery (capsular tear, vitrectomy, etc)
- 3) History of or current retinal conditions or predisposition to retinal conditions
- 4) Amblyopia or strabismus in either eye
- 5) History of or current anterior or posterior segment inflammation of any etiology
- 6) Any form of neovascularization on or within the eye
- 7) Glaucoma (uncontrolled or controlled with medication)
- 8) Optic nerve atrophy
- 9) Subjects with diagnosed degenerative eye disorders
- 10) Postoperative CDVA worse than 0.10 logMAR (20/25 snellen).
- 11) Subjects who have an acute or chronic disease or illness that would confound the results of this investigation in the opinion of the investigator (e.g. immunocompromised, connective tissue disease, clinically significant atopic disease, etc)

EVALUATION CRITERIA:

The main objective of this study is to demonstrate which biometric characteristics can lead to enhanced intermediate or near vision in patients with prior bilateral Eyhance implantation.

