Primary Clinical Endpoints:

- 1) To compare two groups categorized by “distance with minimal intermediate” and “distance with enhanced intermediate/near” based on mean photopic binocular BCDVA and DCIVA (66 cm) of patients with bilateral Eyhance IOLs targeted corrected at plano sphere.
- 2) To determine if any statistically significant differences in biometric data exists between the two groups including pupil size, spherical aberration, q value, etc. that may allow for pre-operative recognition of those patients who could have enhanced benefits of the Eyhance IOL. This will require multiple regression analysis given the large number of variables.
- 3) Comparison of a patient satisfaction survey between the two groups to assess for subjective differences in everyday life to determine if the enhanced vision plays a statistically significant difference in patients’ perceived quality of vision or quality of life.

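### Primary endpoint 2 looks for any significant biometric difference with no error control: about a 25% chance of a false positive if all six planned variables are null and each is tested at 0.05

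*Combined protocol and SAP*

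**What the plan says.** Primary Clinical Endpoints lists three items, with no ranking and no multiplicity rule.

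- **Endpoint 1** compares the two groups "based on mean photopic binocular BCDVA and DCIVA (66 cm) of patients with bilateral Eyhance IOLs targeted corrected at plano sphere". No other outcome is named.
- **Endpoint 2** is "To determine if any statistically significant differences in biometric data exists between the two groups including pupil size, spherical aberration, q value, etc". On method it says only: "This will require multiple regression analysis given the large number of variables".
- **Endpoint 3** compares a satisfaction survey "to determine if the enhanced vision plays a statistically significant difference in" perceived quality of vision or of life.

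Number of Subjects is the only place that gives an alpha (0.05, sidedness not stated) and the only place that counts variables: "Assuming 6 variables (pupil size, q value, spherical aberration, AC depth, axial length, average K power"). It concludes that "approximately 110 patients (220 eyes) will be required". Endpoint 2 does not refer back to those six. Visit Schedule allows pupil size to be photopic and/or mesopic, automated and manual, and no version is chosen for analysis.

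Evaluation Criteria gives the main objective as to "demonstrate which biometric characteristics can lead to enhanced intermediate or near vision". Study Objectives also uses the verb 'demonstrate'.

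Overall Study Design forms the groups on binocular acuity. The minimal-intermediate "group is defined by BCDVA of 0.1 logMAR or better but a DCIVA of 0.4 logMAR or worse"; the enhanced group has the same BCDVA limit and a DCIVA of 0.3 logMAR or better.

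**The concern.** Asking whether any of several variables differs significantly is a union rule: one small p-value is enough for a positive answer, so error accumulates over the variables tested. The list is open-ended, pupil size has several possible versions, and no adjustment, hierarchy or overall test is specified. The wording also leaves unclear whether patients or eyes are the records.

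The stated purpose is to recognise, before surgery, patients likely to gain more from the lens. Followed as written, the plan would let a single chance result among six variables be reported as a demonstrated predictor. A smaller matter is that a difference in DCIVA, which the grouping guarantees, could be listed as a primary result.

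**Working it through.** **Inputs.** From Number of Subjects: alpha 0.05 (taken as two-sided), power 80%, m = 6 variables, 110 patients. From Overall Study Design: DCIVA cut-points 0.3 and 0.4 logMAR. Assumed: one record per patient, and the effect sizes and correlations given below.

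**The plan's own figure.** 50 + 8 × 6 = 98, not 110; read literally as per arm, 2 × 98 = 196. The stated sample size does not reproduce. That is a separate matter: 110 is used below as the plan's number, and the false-positive rates hardly depend on it.

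**False-positive chance, all six variables null.**
- Independent tests: 1 − 0.95⁶ = 0.265.
- Six coefficients in one linear regression, N = 110, simulated (20,000 runs): 0.258, 0.253, 0.248, 0.249 and 0.246 at pairwise predictor correlations of 0, 0.3, 0.5, 0.7 and 0.9.
- Two-group logistic model, N = 110 (6,000 runs), with 50%, 30% or 20% in one group: 0.255 to 0.266.

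So regression leaves the rate near 25% even when the predictors are strongly correlated. It adjusts the variables for one another but does not control error across coefficients.

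Separate two-group comparisons behave differently: 0.243 at correlation 0.3, falling to 0.109 at 0.9. The plan names regression, so the regression figures are the relevant ones.

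**Some variables real.** If three of the six are truly associated, the chance of a false positive among the other three is 1 − 0.95³ = 0.143 (independent tests).

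**Overall model test first.** With an overall test at 0.05 as a gate, the all-null chance of any coefficient claim is about 5%. Once one effect is real the gate tends to open, and the remaining null coefficients are unprotected.

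**With adjustment.** At 0.05/6 = 0.00833 per test, independence gives 1 − (1 − 0.00833)⁶ = 0.049. The simulated rates are 0.046 to 0.047 (linear) and 0.036 to 0.048 (logistic).

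**Power cost of Holm, one true predictor.** Noncentral F with 1 and N − 7 degrees of freedom and noncentrality N × f² / VIF (VIF is the variance inflation factor). The adjusted column uses 0.05/6, Holm's first step.

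| Setting (assumed) | At 0.05 | At 0.05/6 |
|---|---|---|
| N = 110, f² = 0.075, orthogonal | 0.812 | 0.574 |
| N = 110, f² = 0.05, orthogonal | 0.642 | 0.370 |
| N = 110, f² = 0.10, orthogonal | 0.908 | 0.733 |
| N = 110, f² = 0.15, orthogonal | 0.98 | 0.912 |
| N = 110, f² = 0.075, VIF 1.5 | 0.642 | 0.370 |
| N = 90, f² = 0.075, orthogonal | 0.728 | 0.462 |

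The N = 90 row illustrates losing patients whose DCIVA lies between 0.3 and 0.4, who fall in neither group. At f² = 0.075, 166 patients would restore 80% at 0.05/6.

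**Endpoint 1.** DCIVA is at most 0.3 in one group and at least 0.4 in the other, so the group means differ by at least 0.4 − 0.3 = 0.1 logMAR by definition. BCDVA is only capped at 0.1 in both groups, so its difference is not fixed.

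**The case against.** The strongest reply is that this is a single-visit, non-randomised observational study whose second endpoint seeks differences that may help recognise suitable patients. It also names multiple regression precisely because there are many variables, and an analyst might well look at the overall model first. Moreover, the 25% needs all six variables to be null, while the clinical hypothesis is that some of them matter.

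Part of this stands. The 25% is conditional, and the 14.3% and 5% figures show how far the conditions move it. The rest does not answer the point. No overall test is stated, and the plan calls the endpoint primary, seeks significance and speaks of demonstrating, nowhere calling the analysis exploratory. If exploration is meant, the remedy is to say so.

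Four stronger readings are tempting and are not supported:

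- **That 220 eyes will be analysed as independent records.** The error would then be larger (48–65% in simulation, at assumed between-eye correlations of 0.5–0.9). The plan never states that analysis, and the groups are formed on binocular acuity, so this is a reason to name the unit and not part of the size of the fault.
- **That endpoint 1 is a circular significance test.** Unlike endpoints 2 and 3 it mentions no significance, and it may simply introduce the grouping.
- **That endpoint 3 must share the 0.05 with endpoint 2.** Satisfaction is a separate question, and the plan does not say that success on any one endpoint makes the study positive.
- **That Study Objectives makes a softer claim than Evaluation Criteria.** Both use 'demonstrate', and both qualify it.

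**Conclusion.** The point holds for endpoint 2 and should be corrected. With no error control, the chance of at least one false positive is about 25%, provided that all six variables are null, each coefficient is tested at two-sided 0.05, there is one record per patient, and no overall test comes first. It is lower if some variables are real. It is higher if the open list or the extra pupil versions add tests. Naming multiple regression does not change this.

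The endpoint 1 point is minor: the DCIVA gap of at least 0.1 logMAR is built in and is not a finding. Moving endpoint 3 to secondary would be a design choice and not the correction of an error.

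**What to change.** **Endpoint 2.** Before analysis:

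1. Limit the family to the six variables in Number of Subjects, with one pupil measure named.
2. Name group membership as the outcome, with one record per patient (for example, the mean of the two eyes).
3. Report all six coefficients with confidence intervals, whatever their p-values.
4. Label endpoint 2, and every other variable and pupil version, exploratory, and claim no demonstrated predictor.

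These steps need no extra data, visits or patients. The cost is giving up the confirmatory claim.

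**If the claim is kept,** replace the exploratory label on the six variables with Holm at two-sided 0.05 across them. Single-predictor power falls from about 81% to 57% (N = 110, assumed f² of 0.075, orthogonal predictors), below the plan's 80%. It is lower still with correlated predictors or fewer classified patients. The sponsor should weigh that loss, or the 166 patients needed to recover 80% under the same assumptions, against the value of the claim.

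**Endpoint 1 (minor).** Report group sizes, BCDVA and DCIVA descriptively. Do not test DCIVA between the groups or list it as a primary result. This costs nothing.

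**Endpoint 3.** No change is required; ranking it as secondary is optional.

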Maximizing Visual Outcomes with Eyhance IOLs

NCT05611073

25 Jan 2022

PROTOCOL TITLE: Maximizing Visual Outcomes with Eyhance IOLs

STUDY TREATMENTS: None

Study Objectives:

The objective of this study is to demonstrate which pre-operative biometric findings or measurements could indicate increased intermediate or near vision in a patient receiving an Eyhance IOL.

The objective will be completed by measuring visual outcomes at distance, intermediate, and near when corrected to plano sphere as well as obtaining or reviewing biometric measurements in a controlled setting. In addition, the patients will also fill out a questionnaire to determine their level of spectacle independence and satisfaction.

Clinical Hypothesis:

Eyhance IOLs provide intermediate vision based on benchmark defocus curves. Some Eyhance patients also appear to have vastly improved intermediate and even near vision compared to other patients who have received an Eyhance IOL. This study aims to determine which biometric properties (such as spherical aberration, q value, pupil size, etc) can be targeted for these outcomes. Patients will be assessed for corrected monocular and binocular distance, intermediate, and near vision at plano. Lastly patient satisfaction score between the two groups will also be determined.

OVERALL STUDY DESIGN

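### Primary endpoint 2 rests possible pre-operative recognition of patients on statistical significance, which does not show how well patients can be told apart

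*Combined protocol and SAP*

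**What the plan says.** The Study Objectives ask "which pre-operative biometric findings or measurements could indicate increased intermediate or near vision" in patients receiving this lens. Primary Clinical Endpoints, item 2, turns this into a test: "To determine if any statistically significant differences in biometric data exists between the two groups", naming pupil size, spherical aberration and q value among others. It gives the purpose of such differences as something "that may allow for pre-operative recognition of those patients who could have enhanced benefits of the Eyhance IOL". On method it says only: "This will require multiple regression analysis given the large number of variables".

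The groups are defined by the outcome (Overall Study Design). Both have good corrected distance acuity. One has DCIVA of 0.3 logMAR or better and the other 0.4 logMAR or worse. No expected split between them is given.

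The only numerical criteria are in Number of Subjects: "assuming a beta of 0.2 and an alpha of 0.05 for a power of 80" per cent, six predictors, and the statement that "approximately 110 patients (220 eyes) will be required". The protocol gives no AUC, sensitivity, specificity, predictive value, cut-off, minimum useful effect, or internal or external validation.

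**The concern.** Whether two groups differ on average and whether an individual patient's group can be told from a measurement are different questions. A p-value answers the first. It depends on sample size as well as on separation, so it can be small while the two distributions largely overlap. Item 2 joins the two questions in one sentence and supplies evidence only for the first.

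If a variable reaches p < 0.05, the report could describe it as a way of recognising suitable patients before surgery, and readers would have nothing with which to judge that. A weak marker and a strong one would be reported alike.

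**Working it through.** **The plan's own figure.** The stated rule is N = 50 + 8m with m = 6, so 50 + 8 × 6 = 98, or 2 × 98 = 196 if the words "per arm should be sufficient for appropriate power" are taken literally. Neither is 110. A dropout allowance of 10% would give 98 / 0.90 ≈ 109, but none is stated. This is a separate matter. The check below uses 110 and also shows other sizes.

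**Inputs.** From the protocol: 110 patients, alpha 0.05, 80% power, six predictors. Assumed, because not stated: a two-sided test, a normally distributed variable with equal spread in both groups, and the group split (55/55, with a range).

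**Formulas.**
- Smallest significant standardised difference: d = t(0.975, n1 + n2 − 2) × √(1/n1 + 1/n2)
- Difference detectable with 80% power: d80 = (1.960 + 0.842) × √(1/n1 + 1/n2)
- AUC = Φ(d/√2)
- Sensitivity = specificity at the midpoint cut-off (balanced accuracy) = Φ(d/2)

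**At 55/55.** √(2/55) = 0.1907.
- Just significant: d = 1.982 × 0.1907 = 0.378. AUC = Φ(0.267) = 0.605. Correct classification = Φ(0.189) = 57.5%, against 50% by chance. Variance explained = t²/(t² + 108) = 3.5%. At 80% specificity, sensitivity = 1 − Φ(0.842 − 0.378) = 32%.
- 80% power: d80 = 2.802 × 0.1907 = 0.534. AUC = 0.647, with 60.5% correct.

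**Other splits and sizes.**

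| Groups | d, just significant | AUC | Balanced accuracy | AUC at 80% power |
|---|---|---|---|---|
| 55/55 | 0.378 | 0.605 | 57.5% | 0.647 |
| 77/33 | 0.412 | 0.615 | 58.2% | 0.660 |
| 88/22 | 0.472 | 0.631 | 59.3% | 0.682 |
| 99/11 | 0.630 | 0.672 | 62.4% | 0.736 |
| 40/40 | 0.445 | 0.624 | 58.8% | 0.671 |
| 98/98 | 0.282 | 0.579 | 55.6% | 0.611 |

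The 40/40 row is included because patients with DCIVA between 0.3 and 0.4 logMAR belong to neither group, so fewer than 110 may be analysed. At 77/33 the best overall accuracy from a just-significant variable is 0.701, against 0.700 from assigning everyone to the larger group. At 88/22 it is 0.800 against 0.800.

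**A stricter alpha.** Bonferroni for six variables at 55/55 gives d = 0.513 and AUC 0.641, so a smaller alpha does not settle the question.

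**The six-variable model.** A just-significant overall F test at N = 110 corresponds to R² = 0.113 and an apparent AUC of 0.69. After adjustment (R² = 0.061) the AUC is 0.64. In 2,000 simulated studies with one real variable (d = 0.378) and five noise variables at 55/55, the apparent AUC averaged 0.66 and the AUC in new patients 0.57. The plan does not propose an apparent AUC. These figures show why one added later must be corrected for optimism.

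**What good discrimination would need.** At 55/55, an AUC of 0.70 needs d = 0.74 (p about 0.0001), and an AUC of 0.80 needs d = 1.19.

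**Why a lower limit above 0.5 is not enough.** By the Hanley-McNeil formula at 55/55, an AUC of 0.605 has standard error 0.054 and 95% CI 0.605 ± 1.96 × 0.054, that is 0.500 to 0.711. For a single marker, requiring the lower limit to exceed 0.5 therefore almost repeats the significance test.

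**The case against.** The strongest reply is that the text is hedged. Differences may allow recognition, measurements could indicate better vision, and the main objective under Evaluation Criteria concerns which characteristics can lead to it. These can fairly be read as association aims in a single-centre observational study, for which regression is a conventional first step. That stands in part. A reader might infer that the plan commits to selecting patients on p-values alone, but it declares no classifier, cut-off or selection rule. What remains is that recognition is written into a primary endpoint and significance is the only evidence named for it.

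A second reply is that the figures describe a boundary case: one variable, exactly at p = 0.05, in a two-group comparison, whereas the plan specifies multiple regression. That also stands. A reader might infer that any significant marker here would misclassify about four patients in ten. The documents do not support this, because that figure (100% − 57.5% = 42.5%) belongs to a single just-significant variable in balanced groups, and a larger effect or several good predictors together could do much better. Yet the 80%-power effect reaches only 0.65 at 55/55, and the plan has no way of reporting which case has occurred.

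**Conclusion.** The point holds in a limited form. Item 2 links possible pre-operative recognition to significant group differences and plans nothing that measures how well patients are separated. At 55/55 a just-significant single variable has an AUC of about 0.61, and the 80%-power effect about 0.65. The just-significant value is 0.62 to 0.67 at splits from 77/33 to 99/11. These values rest on normality, equal spread, a two-sided test and assumed splits.

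The association analysis is not invalidated by this. The gap lies between that analysis and any statement about recognising patients.

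The word pre-operative needs separate care. The Visit Schedule has one visit, after surgery, at which pupil size and iDesign are measured. Only the IOL Master or Atlas biometry may be reviewed rather than remeasured, and a remeasured value is also post-operative. The documents do not show that pre-operative values will exist for every predictor.

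**What to change.** - Keep the regression p-values, and state that they address association only.
- For the prespecified six-variable model ("Assuming 6 variables (pupil size, q value, spherical aberration, AC depth, axial length, average K power"), report the bootstrap optimism-corrected AUC for the two groups, or the corrected R² for continuous DCIVA, with a 95% CI. Add sensitivity and specificity at a cut-off stated in advance.
- Prespecify and justify a minimum useful AUC, and say whether the corrected estimate or its lower confidence limit must reach it. A lower limit above 0.5 should not be the criterion. If the minimum is not met, limit the conclusion to association.
- Restrict any claim about pre-operative use to a model containing only predictors with values recorded before surgery, and state for each predictor when it was measured.

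The discrimination measures need only a little more analysis code and some wording, using data the study already collects. That does not extend to pre-operative pupil or iDesign values: if they are not on record, the pre-operative claim has to be narrowed. The other cost is that predictive performance will look less favourable than the p-values suggest. With a CI half-width of about 0.105 at an AUC of 0.605 and a 55/55 split, it will also be visibly imprecise.
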